1.5.2 Serlopitant Clinical Summary

In humans, serlopitant has been administered to over 1000 individuals. Single doses up to 400 mg have been well tolerated in young adult males and single doses up to 25 mg have been well tolerated in the elderly. Multiple doses of up to 50 mg a day for 4 weeks have been well tolerated in healthy young males, and a single (loading) dose of 15 mg followed by daily doses of 5 mg for 2 weeks have been well tolerated in elderly males and females. Forty-one (41) subjects received 4 mg liquid filled capsule (LFC) daily (bioequivalent to 5 mg tablets) for 1 year. Plasma concentrations of serlopitant appear to increase in a dose-proportional fashion in both young males and elderly subjects (males and females). Peak plasma concentrations after a single oral dose occurred at ~2 to 4 hours in both young and elderly subjects. A single loading dose of up to 15 mg followed by 6 to 8 weeks of up to 5 mg daily doses has been well tolerated in adults with chronic pruritus and PN.

Pharmacokinetic data demonstrate good plasma exposures with oral dosing, linear dose-dependent increases in plasma concentration and systemic exposure, a plasma $t_{1/2}$ appropriate for once daily dosing, and mild effects of concomitant food ingestion. Central nervous system (CNS) positron emission tomography (PET) studies have demonstrated good CNS penetrance and > 90% NK1 receptor occupancy (RO) at plasma exposures anticipated to be safe and well tolerated. Three long-lived active hydroxylated metabolites are observed in humans: M1/M1a (L-001256771), M2/M2a (L-001194442), and M3 (L-001426583). These metabolites were present at lower concentrations and were 2- to 9-fold less potent in vivo than the parent compound. The integrated pharmacokinetic/pharmacodynamic (PK/PD) analysis concluded that these metabolites are unlikely to contribute significantly to occupancy of the CNS NK₁-R in humans.

1.5.3 Serlopitant in Pruritus-Related Studies

Serlopitant has been evaluated in two completed Phase 2 studies of subjects with chronic pruritus (TCP-101 and TCP-102).

TCP-101

TCP-101 was a double-blind, placebo-controlled, multi-center study that compared serlopitant 0.25 mg, 1 mg, or 5 mg vs. placebo for the treatment of chronic pruritus. A total of 257 adult subjects 18-65 years of age with chronic pruritus were randomized to receive one of the four dose groups in a 1:1:1:1 randomization. Subjects received a loading dose of 3 tablets on Day 1 and thereafter received 1 tablet per day for 6 weeks. The primary efficacy endpoint was itch severity as measured on a VAS, summarized as a percentage change from baseline.

Mean percent decreases from Baseline in VAS score were larger in the active-treatment groups versus placebo at every scheduled post-baseline study visit. Overall, the results were the most profound for the serlopitant 1 mg and 5 mg groups. For the percent change from Baseline in VAS pruritus scores (the primary efficacy variable), the Week 6 pairwise least

squares mean difference compared to placebo was 5.8 mm, 13.2 mm, and 14.2 mm for serlopitant 0.25 mg, 1 mg, and 5 mg, respectively.

The frequency of treatment-emergent adverse events (TEAEs) and study drug related adverse events (AEs) was higher in the serlopitant 1 mg and 5 mg groups compared to the serlopitant 0.25 mg group, and the frequency in all three treatment groups were higher than in the placebo group. The frequency of AEs leading to study drug discontinuation was comparable in the serlopitant 5 mg and placebo group and higher than in the serlopitant 0.25 mg and 1 mg groups. There was one serious adverse event (SAE) reported in the serlopitant 1 mg group (spontaneous abortion, considered not related). There were no deaths. The most common AEs in the serlopitant groups were diarrhea (6.2%, 1 mg group), upper respiratory tract infection (4.7%, 0.25 mg group), somnolence (4.7%, 5 mg group), nasopharyngitis (4.6%, 1 mg group), headache (4.7%, 5 mg group), urinary tract infection (3.1%, 5 mg group), dry mouth (3.1%, 1 mg group), nausea (3.1%, 1 mg group), arthralgia (3.1%, 0.25 mg group), musculoskeletal pain (3.1%, 1 mg group) and pruritus (3.1%, 1 mg group). The most common AEs in the placebo group were headache (6.3%), nasopharyngitis (3.2%), upper respiratory tract infection (3.2%), urinary tract infection (3.2%) and asthma (3.2%).

TCP-102

TCP-102 was a randomized, double-blind, placebo-controlled multi-center study that evaluated serlopitant 5 mg vs. placebo for the treatment of PN. A total of 128 adult subjects 18-80 years of age with PN were randomized to receive serlopitant or placebo in a 1:1 randomization. Subjects received a loading dose of 3 tablets on Day 1 followed by 1 tablet per day for 8 weeks. The primary efficacy endpoint was the average VAS score as recorded at the study visits. Results at Week 4 and Week 8 were the primary timepoints.

Serlopitant 5 mg was superior to placebo for the reduction of pruritus as measured by change in average VAS from baseline. For the primary endpoint, change from baseline at Week 4 and Week 8 by repeated measures analysis, the decrease from baseline was significantly greater in the serlopitant group than the placebo group, with a mean difference (serlopitant minus placebo) of -1.0 at Week 4 and -1.7 at Week 8. The mean difference at Week 2 was also significant, -0.9. In a post-hoc analysis of the percentage of subjects who were 4-point responders on average VAS at Week 8, 25.0% of placebo subjects and 54.4% of serlopitant subjects were 4-point responders.

TEAEs were reported for 71.9% of serlopitant-treated subjects and 61.9% of placebo-treated subjects. The most frequently reported TEAEs in the serlopitant group were nasopharyngitis (17.2% serlopitant, 3.2% placebo), diarrhea (10.9% serlopitant, 4.8% placebo), and fatigue (9.4% serlopitant, 6.3% placebo). Treatment-related TEAEs were reported for 48.4% of serlopitant-treated subjects and 34.9% of placebo-treated subjects. The most frequently reported treatment-related TEAEs in the serlopitant group were fatigue (7.8%) and diarrhea, peripheral edema, dizziness, and headache (each 6.3%). Most TEAEs were mild or moderate; severe TEAEs were reported for 9.4% of serlopitant-treated subjects and 4.8% of placebo-treated subjects. There were no deaths during the study. Five subjects (3 serlopitant, 2 placebo) had SAEs. The SAEs were actinic elastosis, depression, dizziness, and vertigo in

the serlopitant group; and bradycardia, syncope, respiratory failure, and neurodermatitis in the placebo group. Nine subjects (3 serlopitant, 6 placebo) discontinued due to TEAEs.

No clinically relevant changes were observed in chemistry, hematology, vital signs, or electrocardiogram (ECG) results.

Potential Risks and Benefits: The results of the Phase 2 studies in PN and chronic pruritus, together with the extensive nonclinical and clinical safety data and experience with serlopitant to date and the scientific rationale for NK₁-R inhibition in the treatment of pruritus, serve to support further evaluation of serlopitant for the treatment of pruritus in patients with PN. The potential benefits of continued clinical study outweigh the potential risks.

Please refer to the Investigator's Brochure (IB) for further information regarding serlopitant.

2 STUDY OBJECTIVES

The efficacy objective of this study is to assess the efficacy of serlopitant for the treatment of pruritus in adults with PN.

The safety objectives of this study are to assess the safety and tolerability of repeated oral doses of serlopitant in adults with PN, and to assess whether serlopitant produces physical dependence.

3 STUDY DESIGN

3.1 Overall Study Design

This is a double-blind, randomized, placebo-controlled study to assess the efficacy, safety, and tolerability of serlopitant for the treatment of pruritus in adults with PN. The study will be conducted at approximately 50 study sites. Subjects who meet the study entry criteria will be randomized in a 1:1 ratio to receive daily oral doses of serlopitant 5 mg or placebo for 10 weeks. After completion of the treatment period or early discontinuation of study drug treatment, all subjects will enter a 5-week follow-up (post-study drug observation) period.

This study will consist of three periods, for a total study period of 19 weeks:

- Screening period: 2-4 weeks
- Treatment period: 10 weeks
- Follow-up period: 5 weeks

Informed consent will occur prior to any protocol-mandated procedures, including the stopping of any excluded therapies. This may occur prior to the Screening visit.

During the screening period, all subjects will undergo eligibility evaluation and will be assessed for chronic pruritic conditions frequently associated with PN. Subjects who present

with idiopathic PN at screening may require additional assessments as deemed necessary by the investigator (e.g. endomysial antibody with reflex to titer for subjects with signs or symptoms of dermatitis herpetiformis, skin biopsy for subjects with signs or symptoms of bullous pemphigoid or cutaneous T-cell lymphoma, urea breath test for *Helicobacter pylori*, or allergy testing).

All screening procedures must be completed within 31 days before the Baseline visit. The minimum screening period for all subjects is 14 days to allow for collection of electronic diary (eDiary) screening data. Subjects who require screening period longer than 14 days will have a telephone contact at least 15 days prior to the scheduled Baseline visit to remind them to complete the eDiary as previously instructed at the Screening visit.

Screening procedures may be deferred following discussion with the medical monitor should more than 31 days be required (e.g. to wash out of certain excluded therapies or to treat their underlying condition).

Screening procedures may be repeated (i.e., the subject may be rescreened) following discussion with the medical monitor should the subject have had difficulty complying with eDiary assessments, require further training in the assessments, or have other relevant needs that may delay enrollment in the study but are not expected to impact safety or efficacy assessments.

Subjects will be provided an eDiary at the Screening visit. Subjects must be willing and able to complete the eDiary every day within a consistent timeframe, and comply with restrictions on allowable concomitant therapies, for the duration of the study.

At the Baseline visit (Day 1), eligible subjects will be randomly assigned to receive study drug (serlopitant 5 mg or placebo). Subjects will take a loading dose (3 tablets taken orally) at the site on the first day of the treatment period (Day 1). Starting on Day 2, subjects will take one tablet per day. Study drug may be taken with or without food.

The primary efficacy endpoint will be assessed at Week 10 of treatment.

Subjects who complete the 10-week treatment period and required follow-up period may be given the opportunity to enroll in a one-year open-label safety study (MTI-107) with daily oral doses of serlopitant 5 mg.

3.2 Rationale for Study Design and Dose Selection

In the TCP-102 study in patients with PN, serlopitant 5 mg taken daily for 8 weeks was superior to placebo for the reduction of pruritus, in both the overall study population as well as the subgroup of subjects with an atopic diathesis. Similarly, in the TCP-101 study in patients with chronic pruritus, serlopitant 5 mg and 1 mg taken daily for 6 weeks were superior to placebo for the reduction of pruritus, in both the overall study population and the subgroup of subjects with an atopic diathesis.

In both the TCP-102 and TCP-101 studies, serlopitant was generally well-tolerated and demonstrated an overall favorable safety profile at the doses evaluated.

The current MTI-105 study is designed to confirm the efficacy, safety, and tolerability of serlopitant for the treatment of pruritus in patients with PN. The 5 mg dose of serlopitant was selected for this study based on the favorable efficacy, safety, and tolerability profile of serlopitant at this dose level. Over 250 subjects have been exposed to serlopitant at doses of 5 mg tablet-equivalent daily for at least 6 weeks, and ~ 40 subjects have been exposed up to one year. Human CNS PET RO data for serlopitant in healthy young males (Study P002) demonstrated that a serlopitant 5 mg LFC once daily dose is likely to achieve ~ 94% NK₁ RO at steady state.

3.3 Study Endpoints

3.3.1 Primary Efficacy Endpoint

The primary efficacy endpoint is the Worst-Itch Numeric Rating Scale (WI-NRS) 4-point responder rate at Week 10.

3.3.2 Key Secondary Efficacy Endpoints

The key secondary efficacy endpoints are as follows:

- WI-NRS 4-point responder rate at Week 4
- WI-NRS 4-point responder rate at Week 2

3.3.3 Additional Secondary Efficacy Endpoints

Additional secondary efficacy endpoints are as follows:

- Change from baseline in WI-NRS to other timepoints
- WI-NRS 3-point responder rate at Weeks 2, 4 and 10
- Change from baseline in Dermatology Life Quality Index (DLQI) to Week 10
- Change from baseline in DLQI Question 1 to Week 10
- Change from baseline in Investigator's Global Assessment of PN Activity (IGA PN-A) to Weeks 2, 4 and 10
- Change from baseline in Investigator's Global Assessment of PN Stage (IGA PN-S) to Weeks 2, 4 and 10

3.3.4 Safety Endpoints

Safety endpoints are as follows:

- Incidence of TEAEs and SAEs
- Change from baseline in clinical laboratory parameters following study drug exposure

- Change from baseline in vital sign and ECG parameters following study drug exposure
- Change from baseline in the Hospital Anxiety and Depression Scale (HADS)
- Change from baseline in the Epworth Sleepiness Scale (ESS)
- Assessment of physical dependence following study drug exposure, in the 5-week post-drug observation period

3.4 Safety Review

3.4.1 Safety Monitoring Team

An internal safety monitoring team consisting of representatives from Menlo Therapeutics Inc. and its designees will monitor blinded safety data on a regular basis throughout the study.

4 SELECTION OF STUDY POPULATION

4.1 Study Population

Approximately 280 adult subjects with pruritus associated with PN will be enrolled in this study.

Unless otherwise specified by the Institutional Review Board (IRB), subjects may elect to continue study participation under the prevailing version of the study protocol at the time of their initial informed consent.

4.2 Inclusion Criteria

Subjects must meet the following criteria to be randomized into the study:

1. Male or female, age 18 years or older at consent.
2. A diagnosis of PN, defined by the presence of at least ten pruriginous nodules secondary to chronic pruritus present on at least two different body surface areas (e.g. both arms, one arm and one leg, one arm and the anterior trunk, or anterior and posterior trunk).
3. The worst pruritus is identified to be within the areas of the PN lesions.
4. Subject has idiopathic PN OR the subject has an identified pruritic condition associated with the PN and has persistent pruritus despite at least 6 weeks of optimized and stable treatment of the underlying condition prior to the Baseline visit, and is willing to continue the treatment during the study. Please refer to [Section 5.7.1](#).
5. WI-NRS score ≥ 7 in the 24-hour period prior to the Screening visit.
6. Average weekly WI-NRS score ≥ 6.5 in each of the 2 weeks (14 days) immediately prior to Baseline visit, as recorded in the eDiary.

7. All female subjects who are of childbearing potential must be willing to practice highly effective contraception (i.e., pregnancy prevention method with a failure rate of < 1% per year) from the time of the Screening visit until 5 weeks after last dose of study drug. Please refer to [Section 7.1.5](#) for acceptable methods of contraception.
8. Willing and able (as demonstrated by a $\geq 70\%$ eDiary completion rate in the two weeks prior to Baseline visit) to complete daily eDiary entries within a consistent timeframe for the duration of the study.
9. Willing and able (has adequate cognitive ability, in the investigator's opinion) to comply with study visits and study related requirements including providing written informed consent.

4.3 Exclusion Criteria

Subjects who meet any of the following criteria are not eligible for participation in the study:

1. Prior treatment with serlopitant.
2. Active pruritic skin disease, other than PN, within 6 months prior to randomization (with the exception of acute dermatoses such as contact dermatitis, sunburn, viral exanthem, which have been resolved for longer than 4 weeks). Please refer to [Section 5.7.1](#).
3. Treatment with any of the following therapies within 4 weeks prior to randomization.
 - a. Other NK₁-R antagonists (e.g., aprepitant, fosaprepitant, rolapitant).
 - b. Systemic or topical immunosuppressive/immunomodulatory therapies (including but not limited to corticosteroids, phosphodiesterase-4 (PDE-4) inhibitors, cyclosporine, mycophenolate-mofetil, tacrolimus, pimecrolimus, calcipotriene, methotrexate, azathioprine, interferon-gamma, thalidomide, or phototherapy).
 - c. Systemic therapies with recognized anti-pruritic properties (including but not limited to H1 antihistamines, doxepin, gabapentin, pregabalin, cannabinoids, kappa-opioid receptor agonists, and mu-opioid receptor antagonists (e.g. naloxone, naltrexone)).
 - d. Strong CYP3A4 inhibitors (see [Appendix B](#)).
 - e. Use of an indoor tanning facility, or natural sun exposure resulting in significant tanning or sunburn.
4. Treatment with topical anti-pruritic therapies (e.g., menthol, camphor, pramoxine, capsaicin) within 2 weeks prior to randomization (see [Section 5.7.2](#)).
5. Treatment with biologic therapies within 8 weeks or 5 half-lives prior to randomization, whichever is longer.
6. Treatment with any investigational therapy within 4 weeks (8 weeks for investigational biologic therapies) or 5 half-lives prior to randomization, whichever is longer.
7. Serum creatinine, total bilirubin, alanine aminotransferase (ALT) or aspartate aminotransferase (AST) > 2.5 times the upper limit of normal (ULN) during screening.

8. Untreated or inadequately treated thyroid, adrenal, or pituitary nodules or disease or history of thyroid malignancy.
9. History of malignancy within 5 years prior to randomization, with the exception of actinic keratosis, completely treated and non-metastatic cutaneous basal cell carcinoma or squamous cell carcinoma of the skin.
10. Any known major psychiatric diagnosis, such as major depressive disorder, bipolar disorder, schizophrenia, psychotic disorder, intellectual disability, severe alcohol use disorder, which may confound the assessment of serlopitant safety or efficacy, or interfere with the subject's ability to comply with protocol-mandated activities, within 3 years prior to randomization.
11. Suicidal ideation within 3 years prior to randomization, or any history of suicide attempt.
12. Documented history of parasitic infection, including skin parasites such as scabies, within 8 weeks prior to randomization.
13. Presence of any medical condition or disability that, in the investigator's opinion, could interfere with the assessment of safety or efficacy in this trial or compromise the safety of the subject.
14. History of hypersensitivity to serlopitant or any of its components.
15. Currently pregnant or breastfeeding female subject.
16. Planned or anticipated major surgical procedure or other activity that would interfere with the subject's ability to comply with protocol-mandated assessments (e.g. extended international travel) during the subject's participation in the study.

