5 STUDY DRUG

5.1 Study Drug Supply, Route of Administration, and Storage

The study drug in this study is serlopitant 5 mg or placebo in a film-coated tablet formulation for oral administration. The serlopitant tablets contain microcrystalline cellulose, mannitol, croscarmellose sodium, silicon dioxide, sodium lauryl sulfate, and magnesium stearate, and are film coated with Opadry® Brown. The placebo tablets contain microcrystalline cellulose, lactose monohydrate, and magnesium stearate, and are film coated with Opadry® Brown.

The study drug will be provided in bottles that can be stored at room temperature (59-86°F, 15-30°C).

The tablets will be supplied in bottles, with 18 tablets per bottle. One bottle will be issued via Interactive Web Response System (IWRS) at baseline and at Weeks 2 and 4, and two bottles will be issued via IWRS at Week 6. A total of 5 bottles will be dispensed to subjects completing 10 weeks of study drug treatment.

Additional details regarding study drug supplies can be found in the Pharmacy Manual.

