5.3 Dosing Regimen

Subjects will take a loading dose (3 tablets taken orally) at the site on the first day of the treatment period (Study Day 1). Starting on Study Day 2, subjects will take one tablet per day taken orally. Subjects will be instructed to take all doses from Study Day 2 onward once a day. Study drug may be taken with or without food.

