5.8 Assignment to Treatment

5.8.1 *Randomization*

Eligible subjects will be randomized to receive serlopitant 5 mg or placebo in a 1:1 ratio. Stratified permuted block randomization will be used. Randomization will be stratified by the subject's reported WI-NRS score for the 1-week period prior to the Baseline visit (6.5 to < 9, 9 to 10).

An IWRS will be used to perform the randomization.

5.8.2 *Blinding*

This study will be conducted as a double-blind study with the treatment assignment concealed from the subjects, the investigators and their staff, the Sponsor, and any designees of the Sponsor as required. The placebo will be formulated to be indistinguishable from the active study product. Study materials will be packaged and issued in a manner designed to maintain the blind for subjects and all study personnel involved in the direction and execution of study procedures, study assessments, and collection of data. The randomization code for each subject will be available to the sites for use only in an emergency situation. For details of the procedure for unblinding of individual subjects in cases of emergency see [Section 7.6](#).

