8.1 Decision Rule and Sample Size

This study will use a 5% two-sided alpha level. While the alpha level is two-sided, clinically relevant results require a serlopitant benefit. Statistical significance for the key secondary efficacy endpoints requires statistical significance for the primary efficacy endpoint (i.e. stepdown testing from primary to key secondary endpoints). The key secondary efficacy endpoints will be tested in order starting with the Week 4 WI-NRS 4-point responder rate, and then the Week 2 WI-NRS 4-point responder rate.

The target sample size of 280 randomized and dosed subjects (140 per group) has been determined based upon a 1:1 allocation of subjects to treatment groups and a 5% alpha level. Completed Phase 2 studies indicate that placebo responder rates vary between 20% and 25% and serlopitant rates between 33% and 47%. A sample size of 280 subjects provides >90% power assuming a placebo responder rate of **CCI** and a serlopitant rate of **CCI**.

The sample size calculations have been performed in PASS 13 (“[PASS 13 Power Analysis and Sample Size Software](#)” 2014) and use a Chi-Squared test. The primary analysis will control for the stratification factors. It is expected that this unstratified power estimate will under-estimate the true power as it does not take the variance reduction resulting from stratification into account ([Matts 1988](#)).

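### The automatic hypersensitivity exclusion (criterion 14) covers the serlopitant tablet's components but not lactose monohydrate, which is listed only for the placebo tablet

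*Protocol*

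**What the plan says.** Protocol Section 4.3, criterion 14, excludes anyone with a "History of hypersensitivity to serlopitant or any of its components". The synopsis has the same wording. Criterion 13, immediately before it, lets the investigator exclude a person with a medical condition or disability that the investigator judges could endanger that person or disturb the trial's assessments.

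Section 5.1 treats both tablets as study drug and lists their contents separately. For the active tablet: "The serlopitant tablets contain microcrystalline cellulose, mannitol, croscarmellose sodium, silicon dioxide, sodium lauryl sulfate, and magnesium stearate, and are film coated with Opadry® Brown". For the placebo: "The placebo tablets contain microcrystalline cellulose, lactose monohydrate, and magnesium stearate, and are film coated with Opadry® Brown".

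On allocation, Section 5.8.1 states: "Eligible subjects will be randomized to receive serlopitant 5 mg or placebo in a 1:1 ratio". On dosing, Section 5.3 gives three tablets on Day 1 and continues: "Starting on Study Day 2, subjects will take one tablet per day taken orally".

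**The concern.** Criterion 14 is a mandatory rule. The investigator does not have to weigh anything: a history of hypersensitivity to a listed component excludes the person. As worded, the rule reaches one of the two tablets a randomized person may take. Section 5.1 already uses study drug as a term for both tablets, and criterion 14 does not use it.

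The difference would be harmless if every placebo ingredient were also in the active tablet, but one is not. Treatment assignment is also concealed from the investigator (Section 5.8.2), so screening has to work for whichever tablet is assigned. An investigator who applies criterion 14 literally has no prompt to look up the placebo list.

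What is at stake is subject protection: a known risk that can be checked at screening is covered by a firm rule for one arm's tablet and left to discretion for the other's. No estimate or test is at stake.

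**Working it through.** **Step 1: compare the ingredient lists (Section 5.1).**

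| Listed for | Ingredients |
|---|---|
| Both tablets | microcrystalline cellulose, magnesium stearate, Opadry Brown coat |
| Serlopitant only | mannitol, croscarmellose sodium, silicon dioxide, sodium lauryl sulfate |
| Placebo only | lactose monohydrate |

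Criterion 14 reaches the first two rows, since each of those ingredients is a component of the serlopitant tablet. It does not reach the third. Lactose monohydrate is the only listed ingredient outside its scope.

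**Step 2: check the other criteria.** No inclusion or exclusion criterion names lactose or the placebo's components. Criterion 13 is the one route left. It can apply to such a person, but only if the investigator forms the opinion it asks for. The accurate description is therefore *not automatically excluded*.

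**Step 3: probability of exposure.** Inputs: the 1:1 ratio (Section 5.8.1), and the target of 280 with 140 per group (Section 8.1).

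P(placebo) = 1 / (1 + 1) = 140 / 280 = 0.50.

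This reproduces the allocation the plan states.

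**Step 4: extent of exposure.** Inputs: three tablets on Day 1, one per day from Day 2 (Section 5.3), ten weeks = 70 days.

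Tablets = 3 + (70 − 1) × 1 = 3 + 69 = 72.

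This is for full compliance through Day 70. It fits within the supply in Section 5.1: 5 bottles × 18 tablets = 90.

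**Step 5: what cannot be computed.** The documents give neither the amount of lactose per tablet nor how often hypersensitivity to it occurs in this population. The expected number affected is 280 × (proportion with a known history who are not excluded by other means) × 0.50, and the middle term is unknown. A figure would have to be invented, so none is given.

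**Step 6: dependence on the coat.** Both tablets carry the Opadry Brown coat, and its composition is not stated. If it contains no lactose, the gap is as described. If it does, lactose is also a component of the serlopitant tablet, criterion 14 already covers it, and the point falls away.

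**The case against.** The strongest objection is criterion 13. A known hypersensitivity to a tablet ingredient fits its wording readily, and Section 5.1 of the same protocol shows the investigator what the placebo contains. There are also safeguards after randomization: the loading dose is taken on site with post-dose adverse events recorded (Section 6.5.4), and Section 5.6 provides for stopping study drug when continuing may put the person at risk. The Pharmacy Manual, the Investigator's Brochure and the consent form are not available here, and any of them may carry an ingredient warning.

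Much of this stands. It rules out saying that such a person satisfies every criterion and must be enrolled. It does not remove the mismatch. The protocol makes hypersensitivity to one tablet's components a firm exclusion and leaves the other tablet to an opinion that nothing prompts. The later safeguards act only once the person has been exposed.

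A reader might also infer that lactose reactions on placebo would distort the adverse-event comparison. TCP-102 reported diarrhea in 10.9% on serlopitant and 4.8% on placebo (Section 1.5.3), a difference of 6.1 points, and extra placebo events would narrow such a gap. The documents do not support that reading, for three reasons:

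- They do not say that hypersensitivity to lactose monohydrate shows itself as diarrhea, or that the unstated amount per tablet causes any.
- The serlopitant tablet has four listed excipients that the placebo lacks, so no net direction can be claimed.
- Extending criterion 14 would not remove excipient effects in people with no history of hypersensitivity, so that argument is separate from the eligibility wording.

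**Conclusion.** The point holds as a narrow mismatch between criterion 14 and Section 5.1. A person with a known hypersensitivity to lactose monohydrate is not automatically excluded, can be excluded at the investigator's discretion, and if randomized has a 50% chance of taking it daily (72 tablets under full compliance through Day 70).

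This rests on two things: the ingredient lists in Section 5.1 are complete apart from the coat, and the coat contains no lactose. The second is an assumption that the sponsor can settle at once.

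The number affected is unknown and probably very small. Sample size, power, alpha, endpoints and efficacy analyses are unchanged. This is a minor but worthwhile correction made for subject protection. The documents give no basis for a claim of bias in the safety comparison.

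**What to change.** Reconcile criterion 14 with Section 5.1, in both Section 4.3 and the synopsis, so that the hypersensitivity exclusion refers to the components of both study drug tablets, serlopitant and placebo. A cross-reference to Section 5.1 would direct the investigator to both lists. Before editing, the sponsor should confirm the composition of the Opadry Brown coat: if it contains lactose, criterion 14 already covers the ingredient and the edit only clarifies.

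The cost is one phrase in two places and at most a very few extra screen failures. The SAP needs no change.
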